## 10.0 Study Design / Methods

A total of 120 chronic stroke survivors will be recruited for an initial Screening session to determine eligibility for enrollment in the subsequent Aims. From this initial session, 40 stroke survivors will be recruited for Aim 1, and a separate 40 stroke survivors will be recruited for Aim 2. From these 80 participants in Aims 1 and 2, a total of 44 will be recruited for Aim 3. Aim 1 involves a single-session experiment, Aim 2 involves two experimental sessions, while Aim 3 involves an intervention with a total of 10-11 sessions. Participants will be enrolled in this study for a period of a year, allowing time to complete all potential sessions.

In the initial Screening session, participants will walk on an instrumented treadmill for 2-minutes. We will calculate  $\rho_{\text{disp}}$  (a measure of the typical gait stabilization strategy) using LED markers and inertial measurement units placed over participants' legs and pelvis. If  $\rho_{\text{disp}}$  is less than 0.56 (well below control norms), participants will qualify to progress to the subsequent Aims. During the Screening session, we will also quantify the secondary

measures of: Functional Gait Assessment; Activities-specific Balance Confidence scale, Fugl-Meyer Lower Extremity Motor Function subscale; Fugl-Meyer Lower Extremity Sensation subscale; self-selected and fastest-comfortable overground gait speed; fear of falling; fall history. All of these secondary measures are commonly used in clinical practice.

In Aim 1, participants will complete a single-session experiment. We will quantify the cutaneous detection threshold for vibration delivered over the bilateral hip abductors. We will also calculate the lateral sway evoked by vibration of each leg, quantified as the shift in center of pressure while standing on a force plate. Participants will then perform a series of treadmill walking trials. In some of these trials, vibration will be applied to the hip abductors or lateral trunk, while we quantify  $\rho_{\text{disp}}$ .

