In Aim 2, participants will complete two experimental sessions. In the first session, participants will perform a series of treadmill walking trials, across which we will vary the pattern and location of vibration applied over the bilateral hip abductors. We will identify the combination of pattern and location that produces the largest increase in  $\rho_{\text{disp}}$  for each participant. In the second session, participants will again perform a series of treadmill walking trials, across which we will compare the personalized stimulation (optimal pattern and location for this individual) with the standard pattern of stimulation used in prior work.

In Aim 3, participants will complete 10-11 experimental sessions. The first and last session will consist of pre and post assessments, in which we will quantify  $\rho_{\text{disp}}$ , Functional Gait Assessment score, Activities-specific Balance Confidence score, overground self-selected and fastest-comfortable walking speeds, and fear of falling. If Aim 2 reveals that personalized stimulation is superior to standard stimulation, the second session will be used to identify the optimal combination of stimulation pattern and location for each participant. Otherwise, this session will not be performed. The remaining sessions will be training sessions, in which participants will perform a series of walking trials at their self-selected speed. In some trials, hip abductor vibration will be applied on a step-by-step basis. In the Augmented group, this vibration will be scaled to augment sensory feedback providing information about the mechanical state of the pelvis. In the Control group, the magnitude of this vibration will be randomized, providing no additional information.

To reduce the risk of participants falling, participants will wear a harness attached to an overhead rail during all treadmill and overground walking trials. This harness will not support body weight, but would prevent participants from falling in the case of a loss of balance. The vibrating tactors and adhesive used to secure the tactors and LED markers to the skin may produce the risk of minor skin irritation. We will reduce this risk by asking participants if they have had any previous experience of skin irritation in reaction to specific gel or tape types, and by checking the participants' skin after each experiment.

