## 11.0 Data Management

For Aim 1, our first analysis will be correlation-based, testing whether metrics of altered perception or cutaneous cueing are associated with the beneficial effects of sensory augmentation. For each participant, we will quantify four independent variables: cutaneous detection threshold (paretic and non-paretic legs); lateral sway distance evoked by hip abductor vibration (paretic and non-paretic legs). We will also quantify the effect of sensory augmentation during gait as the mean change in paretic  $\rho_{\text{disp}}$  between the Normal and Vibrated Abductors trials ( $\Delta \rho_{\text{disp}}$ ). We will test whether each of the four independent

variables is significantly associated with  $\Delta \rho_{\text{disp}}$ , using an alpha value of 0.0125 to account for multiple comparisons. Our second analysis will involve a repeated measures experimental design – directly testing whether vibration designed solely to provide cutaneous cues (Vibrated Trunk condition) has a smaller beneficial effect than vibration designed to elicit both cutaneous cues and an altered perception of pelvis mechanics (Vibrated Abductors condition). For this analysis, we will use a repeated measures ANOVA to compare mean paretic  $\rho_{\text{disp}}$  values during the Normal, Vibrated Abductors, and Vibrated Trunk trials.

For Aim 2, our primary statistical analysis will compare the average increase in paretic  $\rho_{\text{disp}}$  values during Standard Augmentation and Personalized Augmentation conditions (relative to Normal). We will use a paired t-test to compare these  $\Delta \rho_{\text{disp}}$  values. Secondarily, we will use a repeated measures ANOVA to test for group-wide effects of vibration pattern and location, based on data from the first session.

For Aim 3, our primary statistical analysis will use an independent t-test to determine whether the change in paretic  $\rho_{\text{disp}}$  differs significantly between the Augmented and Control groups.

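### Prior exposure to augmentation differs by source Aim, but Aim 3 neither stratifies allocation by source Aim nor adjusts the primary t-test for it

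*Combined protocol and SAP*

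**What the plan says.** Section 10.0 (Study Design / Methods) sets the source of the Aim 3 sample: "From these 80 participants in Aims 1 and 2, a total of 44 will be recruited for Aim 3". It also sets the number of visits: "Aim 1 involves a single-session experiment, Aim 2 involves two experimental sessions, while Aim 3 involves an intervention with a total of 10-11 sessions".

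Both source Aims apply vibration during walking. For Aim 1, "In some of these trials, vibration will be applied to the hip abductors or lateral trunk". Section 11.0 (Data Management) treats the abductor condition as the augmentation itself: "We will also quantify the effect of sensory augmentation during gait as the mean change in paretic" rho_disp between the Normal and Vibrated Abductors trials. In the second Aim 2 session, "we will compare the personalized stimulation (optimal pattern and location for this individual) with the standard pattern of stimulation used in prior work".

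Within Aim 3, "The first and last session will consist of pre and post assessments". If Aim 2 shows personalised stimulation to be superior, "the second session will be used to identify the optimal combination of stimulation pattern and location for each participant"; if not, that session is dropped. No arm is exempted. The arms differ in the training sessions, where the Augmented group receives scaled vibration and, for the comparator, "In the Control group, the magnitude of this vibration will be randomized, providing no additional information".

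Section 3.0 calls the trial randomised and controlled. Section 11.0 plans 22 per group and an independent t-test on the change in paretic rho_disp. The document names no stratification factor, no covariate for source Aim, no washout and no masking plan.

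**The concern.** The comparator is meant to be vibration that carries no information, yet nobody enters Aim 3 without having felt the informative kind. Section 11.0 expects the benefit to grow with repeated exposure, so it is reasonable to ask whether earlier exposure leaves something behind.

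The amount of earlier exposure is not uniform. Participants from Aim 2 have had two sessions, one of them a search over patterns and locations. Participants from Aim 1 have had one session, in which some trials vibrated the trunk instead. If that difference affects how much a person changes during Aim 3, source Aim is a prognostic factor for the primary endpoint. With 22 per arm, an uneven split on such a factor is not rare, and an unadjusted t-test leaves its effect in the estimate.

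**Working it through.** **1. The plan's own figure.** Inputs from Section 11.0: effect size 1.0, alpha 0.05, power 0.80, 20% dropout. A two-sided two-sample t-test (noncentral t) gives n = 16.71, rounded up to 17 per group, with power 0.807. Dropout: 17 / 0.8 = 21.25, rounded up to 22. The stated 17 and 22 both reproduce.

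**2. Where each exposure falls relative to baseline.**

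| Exposure | Who receives it | Relative to Aim 3 pre-assessment |
|---|---|---|
| Aim 1 (one session) or Aim 2 (two sessions) | Both arms | Before |
| Optimisation session, only if Aim 2 is positive | Both arms | After |
| Training, 8 sessions (10 − 2, or 11 − 3) | Scaled in Augmented, random in Control | After |

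A carry-over effect common to both arms adds the same amount to each mean change and cancels in the difference. A stable gain from Aim 1 or 2 is already in the baseline and is subtracted out. Source Aim therefore matters only if it alters the later change, for example through a ceiling, faster learning or fading of an earlier gain.

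**3. Chance of an uneven split.** The document does not say how many of the 44 come from each Aim. Assume 22 and 22, with unstratified 22:22 allocation. The number X of Aim 2 participants in one arm is hypergeometric: P(X = k) = C(22,k) × C(22,22−k) / C(44,22). Summing both tails:

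- 13 v 9 or worse: 0.366
- 14 v 8 or worse: 0.131
- 15 v 7 or worse: 0.034

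For other mixes, the chance that the arms differ by 6 or more is 0.104 (30 from Aim 1, 14 from Aim 2) or 0.069 (34 and 10). At 40 and 4 a difference of 6 cannot occur.

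**4. Size of the resulting shift.** Shift = (difference in count / 22) × s, where s is the difference in mean change between source Aims, in SD units. The document gives no value for s, so these are assumptions. At 14 v 8 the count difference is 6:

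- s = 0.25: 6/22 × 0.25 = 0.07 SD
- s = 0.5: 6/22 × 0.5 = 0.14 SD
- s = 1.0: 6/22 × 1.0 = 0.27 SD

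At 13 v 9 with s = 0.5 the shift is 4/22 × 0.5 = 0.09 SD. The sign depends on which arm has more Aim 2 participants.

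**5. Possible dilution.** If shared exposure leaves less room for the Augmented arm to improve over Control, the true contrast is smaller. The document gives no carry-over size, so this is illustration only. With 17 completers per group, a 10% reduction (d = 0.9) gives power 0.72 and a 20% reduction (d = 0.8) gives 0.62, compared with 0.81 at d = 1.0. With all 22 per group retained, the corresponding figures are 0.83, 0.74 and 0.90.

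**The case against.** A reader might infer that giving Controls real augmentation before training makes the comparison unbalanced by design. The document does not support that. Allocation is randomised and the optimisation session, if held, is the same in both arms, so the exposure is balanced in expectation. That session is also conditional on the Aim 2 result.

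A reader might also infer that Controls, having felt linked vibration, will recognise the random version. This is possible but not shown. That the Aim 1 and Aim 2 vibration follows the user's mechanics is itself inferred from its being called augmentation, and participants meet several vibration conditions there. The primary endpoint is measured by instruments, so any such effect would chiefly concern the self-reported secondary measures, balance confidence and fear of falling.

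The remaining objection is about size. A 13 v 9 split is minor, and even 14 v 8 under a 0.5 SD assumption moves the estimate by 0.14 SD against a planned effect of 1.0 SD. Expecting benefit from eight training sessions does not imply that one or two earlier sessions leave a material effect. Randomisation alone keeps the t-test valid on average over allocations. All of this stands, and it makes the point a modest one. It does not remove the case for controlling a factor that is known at enrolment, differs by construction and costs almost nothing to handle.

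**Conclusion.** The point holds as a cheap improvement, not as a source of systematic bias. Both arms have earlier exposure to augmentation. Its amount differs by source Aim, and the plan neither stratifies by source Aim nor adjusts for it. Assuming 22 participants from each Aim, a split of 14 v 8 or worse has probability 0.13. An assumed 0.5 SD difference in change by source Aim would then shift the contrast by about 0.14 SD at 14 v 8, in either direction. Both assumptions are ours: the document gives neither the mix of source Aims nor any carry-over size. Dilution of the contrast is possible if gains are retained and saturate, but it cannot be quantified from the document.

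**What to change.** Stratify the Aim 3 randomisation by source Aim (1 v 2). In Section 11.0, replace the unadjusted t-test with a linear model for change in paretic rho_disp that has arm and source Aim as factors. Source Aim is known before allocation, so no new data are needed. The cost is one residual degree of freedom (with 34 completers, 34 − 2 = 32 becomes 34 − 3 = 31) and a slightly more complex allocation list.

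Optionally, ask each participant at the final session which vibration they believe they received, and report the answers as context for balance confidence and fear of falling. This costs one question.

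Moving the optimisation session ahead of the pre-assessment is not recommended on the present information. Both arms receive the session either way, so the move does not remove a bias. Whether it helps precision depends on how long carry-over lasts: a lasting effect would favour the move, and a transient one would put a short-lived after-effect into the baseline. The document does not give that duration.

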## 11.0 Data Management

For Aim 1, our first analysis will be correlation-based, testing whether metrics of altered perception or cutaneous cueing are associated with the beneficial effects of sensory augmentation. For each participant, we will quantify four independent variables: cutaneous detection threshold (paretic and non-paretic legs); lateral sway distance evoked by hip abductor vibration (paretic and non-paretic legs). We will also quantify the effect of sensory augmentation during gait as the mean change in paretic  $\rho_{\text{disp}}$  between the Normal and Vibrated Abductors trials ( $\Delta \rho_{\text{disp}}$ ). We will test whether each of the four independent

variables is significantly associated with  $\Delta \rho_{\text{disp}}$ , using an alpha value of 0.0125 to account for multiple comparisons. Our second analysis will involve a repeated measures experimental design – directly testing whether vibration designed solely to provide cutaneous cues (Vibrated Trunk condition) has a smaller beneficial effect than vibration designed to elicit both cutaneous cues and an altered perception of pelvis mechanics (Vibrated Abductors condition). For this analysis, we will use a repeated measures ANOVA to compare mean paretic  $\rho_{\text{disp}}$  values during the Normal, Vibrated Abductors, and Vibrated Trunk trials.

For Aim 2, our primary statistical analysis will compare the average increase in paretic  $\rho_{\text{disp}}$  values during Standard Augmentation and Personalized Augmentation conditions (relative to Normal). We will use a paired t-test to compare these  $\Delta \rho_{\text{disp}}$  values. Secondarily, we will use a repeated measures ANOVA to test for group-wide effects of vibration pattern and location, based on data from the first session.

For Aim 3, our primary statistical analysis will use an independent t-test to determine whether the change in paretic  $\rho_{\text{disp}}$  differs significantly between the Augmented and Control groups.

Power analyses were performed for each Aim. For Aim 1, the proposed sample size (n=40) was selected to be able to detect a moderate correlation ( $r=0.5$ ) between our input variables and  $\Delta \rho_{\text{disp}}$ . Aim 2 was powered to detect a moderate effect size (Cohen's  $d = 0.5$ ) between Standard and Personalized sensory augmentation methods. For our Aim 3 intervention, we estimate an effect size of 1.0 based on our prior results. It should be noted that we expect this effect to increase with the repeated exposure to sensory augmentation proposed here. With an effect size of 1.0 and an alpha value of 0.05, we will need 17 participants per group for 0.80 power. We propose 22 participants per group to account for 20% dropout.

Steps will be taken to minimize the risk of loss of confidentiality. All data will be stored on a password-protected computer and password-protected secure server that is backed-up nightly.

The RESTORE registry (Pro#00037803), from which this study will recruit subjects, also serves as a data analysis tool by which interdisciplinary teams may share data across projects and provide MUSC's stroke recovery research community with a more complete registry with key stroke elements. Some subjects may have participated or will participate in other stroke related research studies at MUSC. Sharing data from this and other stroke research studies with RESTORE will allow for more targeted recruitment efforts in the future and could reduce the burden placed on subjects by reducing the duplicative efforts of collecting common data and physical function assessments requested by multiple studies and storing them in one centralized and secure location.

Subjects are informed in the consent process if they enroll into the RESTORE registry, their data from this study will be shared. Subjects will be asked to sign a HIPAA authorization stating their health information may be disclosed to MUSC investigators requiring their data for their research projects upon approval by an Institutional Review Board.

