**1.0 Objectives / Specific Aims**

The objective of this project is to develop and test a method of providing real-time augmentation of hip proprioceptive feedback during post-stroke walking. Our central hypothesis is that augmented proprioception will increase the mechanics-dependent modulation of step width, an important gait stabilization strategy. The first aim of this study is to identify the physiological mechanism underlying the beneficial effects of sensory augmentation on step-by-step gait stabilization. Here, we will differentiate between the potential mechanisms of altered perception and cutaneous cueing. The second aim is to determine whether personalizing sensory augmentation methods to individual participants produces greater beneficial effects on post-stroke gait stability. Here, we will identify the optimal combination of vibration pattern and location for each participant, and test whether this personalized stimulation is superior to standard methods. The third aim is to establish the safety, feasibility, and efficacy of a rehabilitation intervention centered on repeated exposure to sensory augmentation during gait. This will be accomplished through a small-scale clinical trial.

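### Optional improvement, not an error: Holm could replace the fixed 0.0125 for the four Aim 1 correlations, keeping the 5% familywise limit and gaining power when several associations are real

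*Combined protocol and SAP*

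**What the plan says.** Section 1.0 gives the purpose of Aim 1 as being to "differentiate between the potential mechanisms of altered perception and cutaneous cueing".

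Section 11.0 describes a first, correlation-based analysis, "testing whether metrics of altered perception or cutaneous cueing are associated with the beneficial effects of sensory augmentation". There are four predictors: cutaneous detection threshold and vibration-evoked lateral sway, each measured on the paretic and the non-paretic leg. Each is tested against the change in paretic ρ_disp, "using an alpha value of 0.0125 to account for multiple comparisons". No stepwise procedure is mentioned. The 5% familywise level is not written out but is implied by 4 × 0.0125.

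A second analysis, a repeated measures ANOVA, compares the Normal, Vibrated Abductors and Vibrated Trunk conditions. There the abductor vibration is described as "designed to elicit both cutaneous cues and an altered perception of pelvis mechanics".

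On size, Section 11.0 says that n = 40 "was selected to be able to detect a moderate correlation" of r = 0.5. It states neither power nor sidedness for Aim 1; the 0.80 power in that section refers to Aim 3.

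**The concern.** The four tests are two mechanisms measured on two legs. The plan describes the abductor stimulus as producing both effects, so true associations in both pairs of predictors cannot be excluded. The fixed threshold costs most in that case: once one association is established, Bonferroni still holds the others to 0.0125, although the familywise limit no longer requires it. In an aim meant to separate mechanisms, a missed second mechanism can make a dual effect look like a single one. The power given up can be recovered at no cost in participants.

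**Working it through.** **Inputs from the documents.** Four tests, 0.0125 each, n = 40, r = 0.5 (all Section 11.0).

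**Assumptions.** Two-sided Pearson tests; a familywise level of 5%; an 80% power target; all 40 participants analysed. The documents do not give the correlations among the predictors. I take the between-leg correlation within one measure as w = 0 to 0.7 and the correlation between the two measures as 0, with 0.3 as a sensitivity check.

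**1. The plan's threshold.** 0.05/4 = 0.0125. Familywise error is at most 5% under any dependence; with independent tests it is 1 − (1 − 0.0125)⁴ = 0.0491.

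**2. The plan's sample size.** Fisher z: atanh(0.5) × √(40 − 3) = 0.5493 × 6.083 = 3.341. The two-sided critical value at 0.0125 is 2.498. Power = Φ(3.341 − 2.498) = 0.801; n = 39 gives 0.788. Solving for n at 80% power gives 39.96, so 40. By contrast, two-sided 0.05 would need only 30, and one-sided 0.0125 only 35. The stated n therefore already pays for the correction.

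**3. What each rule demands of the data.** Critical |r| = t/√(t² + 38), with t on 38 degrees of freedom:

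| Ordered p-value | Fixed rule: alpha, critical abs(r) | Holm: alpha, critical abs(r) |
|---|---|---|
| smallest | 0.0125, 0.391 | 0.0125, 0.391 |
| second | 0.0125, 0.391 | 0.0167, 0.376 |
| third | 0.0125, 0.391 | 0.025, 0.354 |
| largest | 0.0125, 0.391 | 0.05, 0.312 |

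Holm stops at the first non-rejection. No Holm threshold is below 0.0125, so it cannot lose a rejection that the fixed rule makes.

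**4. Size of the gain.** Simulation: multivariate normal data, n = 40, r = 0.5 for each true association, 200,000 data sets per scenario, w = 0, 0.5 and 0.7. A mechanism counts as detected if either of its two legs is significant.

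| True associations | Power per true association, fixed → Holm | Both mechanisms detected, fixed → Holm |
|---|---|---|
| one | 0.81 → 0.81 | not applicable |
| two, one leg of each measure | 0.81 → 0.83 | 0.65 → 0.70 |
| three | 0.81 → 0.86 | 0.73–0.79 → 0.80–0.85 |
| four (w = 0.5 to 0.7) | 0.81 → 0.90 | 0.81–0.86 → 0.88–0.92 |

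Four true associations at w = 0 is left out because it implies R² = 1. With 0.3 between measures the results are similar (one leg of each true: 0.67 → 0.72). The chance of detecting at least one true association changes by about 0.1 point or less. No rejection made by the fixed rule was lost under Holm in any scenario.

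**5. Size of the cost.**

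| Scenario | Fixed → Holm |
|---|---|
| One mechanism real, both legs true: flagged alone | 0.88–0.95 → 0.87–0.93 (down 1.7–1.9 points) |
| One mechanism real, one leg true: flagged alone | 0.79–0.80 → 0.78–0.79 (down 0.6–0.7 point) |
| False rejection of any null predictor, none true | 4.3–4.9% under both |
| False rejection, one true | 3.4–3.7% → 4.2–4.7% |
| False rejection, two true | 2.2–2.5% → 3.8–4.4% |
| False rejection, three true | 1.2–1.3% → 3.7–4.1% |

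**The case against.** The plan prespecifies a valid rule and sizes Aim 1 consistently with it, so choosing another valid rule is partly preference. That is right, and it is why this is only an optional point.

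The gain also requires both mechanisms to be real. The description of the stimulus does not show that differences between participants in both metrics predict response. If one mechanism operates, Holm isolates it slightly less often, and with two true associations false rejection nearly doubles, though it stays under 5%. All of this stands.

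The favourable scenarios are demanding. With r = 0.5 for every true predictor and no correlation between measures, the implied joint R² is 0.50–0.98 (one leg of each), 0.67–0.78 (three true) and 0.59–0.67 (four true, w = 0.5 to 0.7). Section 11.0 does not claim that several predictors reach 0.5. At r = 0.4, however, the gain in detecting both mechanisms is still about 5 to 10 points. At r = 0.3 it is about 2 to 6 points, on bases of only 7–21%. The benefit shrinks but remains.

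Finally, under Holm the verdict on one predictor depends on the p-values of the others: a threshold correlation of 0.36 may count or not depending on the sway results. The fixed rule gives every test its own cutoff and a matching 98.75% interval. This is a legitimate reason to keep the fixed rule, but the plan specifies no such intervals, so nothing it promises is disturbed.

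**Conclusion.** The concern holds as an optional improvement. The fixed 0.0125 controls familywise error, and n = 40 is consistent with it. Holm keeps the same 5% limit and, at r = 0.5, adds about 5 to 7 points to the chance of detecting both mechanisms when both are real. It adds about 2, 5 and 9 points of power per association with two, three and four true associations, and practically nothing with one. The price is a loss of up to about 2 points in isolating a single real mechanism, and false rejection closer to the 5% limit, though never above it.

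These sizes rest on the assumed sidedness, complete data on 40 participants and the assumed correlations among predictors. The familywise guarantee and the fact that no rejection is lost do not depend on those assumptions. The ANOVA in the same section compares the trunk and abductor conditions directly, which limits how much turns on the four correlations.

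**What to change.** Before Aim 1 data are analysed, replace the fixed 0.0125 in Section 11.0 with: *using the Holm step-down procedure at familywise alpha 0.05 across the four correlations*. The first Holm step is still 0.0125, so the n = 40 justification stands. No extra participants or data are needed. What the team accepts in return is that significance for one predictor depends partly on the other three. A team that prefers a separate cutoff for each correlation can keep the present rule without fault.

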### 3.0 Intervention to be studied

In this study, Aims 1 and 2 do not involve an intervention, instead including cross-sectional mechanistic experiments. Aim 3 will test the safety, feasibility, and efficacy of a novel intervention involving low-intensity vibration applied over the bilateral hip abductor muscles of chronic stroke survivors during walking. This Aim will take the form of an early-stage, small-scale (n=44 participants) randomized controlled clinical trial.

The precise intervention to be studied is novel, as the vibration amplitude applied during walking will be directly controlled by the user's walking mechanics, allowing us to augment the sensory information available to users. However, the method and form of the vibration itself is not novel. Many prior studies have used vibrating motors (as in the present study) to deliver the same type of mechanical vibration to clinical populations during the performance of functional movement tasks (e.g. reaching, standing, walking) [14-17]. We ourselves have published work investigating the effects of mechanical vibration [11, 18-19], and have an IRB-approved project that involves these methods (Pro00046775).

No medication is involved in the intervention, and FDA approval will not be required for the use of our vibrating tactors, which deliver minimal mechanical energy to users – instead simply evoking a sensory response.

The rationale for the intervention is to use non-invasive methods (vibration) to improve the sensory accuracy of chronic stroke survivors. This low-risk method could have the potential to produce large improvements in patient functional mobility. While we have observed no adverse events in the use of these methods, and no such adverse events have been reported in the literature due to the use of these methods, one of the goals of this project will be to definitively establish the safety of this intervention.

For the intervention, the control group will receive vibration applied over the bilateral hip abductors, just as the experimental group. However, the vibration will not be linked to the user's mechanics, instead being randomly delivered – a method that has been used previously [11].

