### 4.0 Study Endpoints

For the intervention in Aim 3, our outcome measure of safety will be the proportion of participants who experience an adverse event potentially related to the intervention (e.g. skin irritation; falls) or any serious adverse event (e.g. hospitalization; death). Our primary measures of feasibility will be participant adherence (percentage of training sessions attended) and drop-out (non-attendance of final assessment session). We will also track the total walking time across training sessions (of a maximum possible 312 minutes). Our primary measure of efficacy will be changes in  $\rho_{\text{disp}}$ , a metric that quantifies the extent to which participants effectively stabilize their gait by adjusting their step width to account for pelvis dynamics [20]. Our secondary measures of efficacy will be the common clinical measures of Functional Gait Assessment score, Activities-specific Balance Confidence score, overground gait speed, and fear of falling.

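### The Aim 3 primary t-test on change in paretic rho_disp is valid but leaves out the baseline value; prespecifying adjustment for it would usually give a more precise answer at almost no cost.

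*Combined protocol and SAP*

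**What the plan says.** Section 4.0 (Study Endpoints) defines efficacy for Aim 3: "Our primary measure of efficacy will be changes in" rho_disp. Section 10.0 (Study Design / Methods) sets the measurement times: "The first and last session will consist of pre and post assessments", with rho_disp measured at both. Section 11.0 (Data Management) gives the whole primary analysis in one sentence: "For Aim 3, our primary statistical analysis will use an independent t-test to determine whether the change in paretic" rho_disp differs between the two groups. No covariate is named, and no adjusted analysis appears as primary, secondary or sensitivity.

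Section 3.0 describes the design: "This Aim will take the form of an early-stage, small-scale (n=44 participants) randomized controlled clinical trial". Section 11.0 sizes it: "For our Aim 3 intervention, we estimate an effect size of 1.0 based on our prior results", then "With an effect size of 1.0 and an alpha value of 0.05, we will need 17 participants per group for 0.80 power", then "We propose 22 participants per group to account for 20% dropout". It gives no standard deviation, no pre-post correlation and no scale for the effect size.

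**The concern.** Analysing change assumes that each unit of difference at the pre-assessment carries over in full to the post-assessment, that is, a slope of 1. The actual slope is r × SD_post / SD_pre. If it is below 1, a group that starts lower by chance tends to show a larger change whatever the treatment does, and the t-test does not correct for this.

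With about 17 to 22 analysed per group, chance baseline differences can be sizeable. The value needed to correct for them is already available for everyone who has a change score. What is at stake is the width of the confidence interval and the power, not the validity of the test.

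**Working it through.** **Inputs from the documents (section 11.0).** Effect size d = 1.0, alpha 0.05, power 0.80, 17 per group, 20% dropout, 22 per group.

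**Assumptions.** d is on the change-score scale; the test is two-sided; pre and post SDs are equal (k = SD_post / SD_pre = 1) unless stated; r is taken from 0.3 to 0.9; allocation is not stratified on baseline rho_disp (no allocation method is described).

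**1. The plan's own figure.** For the two-sample t-test the noncentrality is d × √(n/2). At n = 17 it is √8.5 = 2.92 on 32 degrees of freedom, which gives power 0.807; n = 16 gives 0.781. So 17 is correct. A one-sided test would need only 14, so the plan is two-sided. Dropout: 17 / 0.8 = 21.25, rounded up to 22. At 22 per group power is 0.900. Both stated sample sizes reproduce.

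**2. Variance of the adjusted estimate relative to the change score.** The large-sample ratio is k²(1 − r²) / (1 + k² − 2rk), which is (1 + r)/2 when k = 1. Estimating the slope multiplies it by 1 + 1/(2n − 4), which is 31/30 at n = 17. Power for the adjusted analysis uses the noncentral t with 2n − 3 degrees of freedom, averaged over chance baseline imbalance.

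| r (k = 1, n = 17) | Variance ratio | Fall in standard error | Adjusted power, d = 1.0 | t-test power |
|---|---|---|---|---|
| 0.3 | 0.65 × 31/30 = 0.672 | 18% | 0.931 | 0.807 |
| 0.5 | 0.75 × 31/30 = 0.775 | 12% | 0.894 | 0.807 |
| 0.7 | 0.85 × 31/30 = 0.878 | 6% | 0.854 | 0.807 |
| 0.9 | 0.95 × 31/30 = 0.982 | 1% | 0.814 | 0.807 |

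Simulation with 40,000 trials per setting agrees with these powers to within about 0.002, and gives a type I error of 0.049 to 0.051 for both analyses.

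With no dropout (22 per group, d = 1.0) adjusted power is 0.977 / 0.958 / 0.934 / 0.907 at the same four values of r, against 0.900. If the true effect were 0.8, a scenario not in the plan, power at 17 per group would run from 0.787 (r = 0.3) through 0.728 (r = 0.5) to 0.626 (r = 0.9), against 0.619.

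**3. Where the gain ends.** With equal SDs, break-even solves (1 + r)/2 × 31/30 = 1, so r = 60/31 − 1 = 0.935. With k = 1.2 at 17 per group and d = 1.0:

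| r (k = 1.2, n = 17) | Variance ratio | Adjusted power | t-test power |
|---|---|---|---|
| 0.5 | 0.90 | 0.845 | 0.807 |
| 0.7 | 1.00 | 0.807 | 0.807 |
| 0.8 | 1.03 | 0.795 | 0.807 |
| 0.9 | 1.01 | about 0.80 | 0.807 |

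The worst case is a slope of exactly 1: variance ratio 31/30 = 1.033 and power 0.794.

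**4. The same gain seen as baseline imbalance.** The chance difference in group means at baseline has SD √(2/17) = 0.343 baseline SDs, and it exceeds 0.5 SD in either direction with probability 0.145. With k = 1, an imbalance of one such SD shifts the expected difference in change by (1 − r) × 0.343 / √(2 − 2r) change-score SDs: 0.20 / 0.17 / 0.13 / 0.08 at r = 0.3 / 0.5 / 0.7 / 0.9. This is part of the variance removed in step 2, not a further benefit to be added to it.

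**The case against.** The planned test controls its error rate, matches the declared endpoint and is correctly sized, so the choice could be called a preference between two valid analyses in a small early-stage trial. That stands as a limit on severity: nothing here is wrong, and on the plan's own effect size the power is already adequate.

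The size of the gain also rests on quantities the documents do not give. If responses to training vary enough to make the post SD larger than the pre SD, correlations of 0.7 to 0.8 leave no gain or a slight loss. This stands too, and it is why the claim is limited to usually. Two things weigh on the other side. The loss is capped at about 3% of variance, whereas the gain can reach 12 power points. And section 10.0 admits only people with screening rho_disp below 0.56; selecting on the outcome measure narrows its range and tends to lower r, which favours adjustment. That gives a direction, not a size.

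The imbalance figures assume allocation not stratified on baseline rho_disp, and would shrink if it were. The point that the endpoint is change does not count against adjustment: with baseline in the model, the group coefficient is the same whether the outcome is post or change.

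**Conclusion.** The concern holds as a recommended improvement in efficiency, not as the correction of an error. At 17 analysed per group, with equal SDs and d = 1.0 on the change scale, adjustment cuts the standard error by about 18% at r = 0.3 down to 1% at r = 0.9, and raises power from 0.807 to between 0.931 and 0.814. There is no gain when the slope of post on pre is close to 1 (r above about 0.935 with equal SDs, or from r = 0.7 upward when the post SD is 1.2 times the pre SD). The correlation, the SD ratio, the effect-size scale and unstratified allocation are all assumptions. Adjustment does not deal with the exclusion of voluntary withdrawals in section 13.0, which is a separate matter.

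**What to change.** Before outcome data are seen, replace the Aim 3 sentence in section 11.0 with a linear model of post-assessment paretic rho_disp (or, equivalently, its change) on group, with pre-assessment paretic rho_disp as covariate. Report the adjusted group difference with its 95% confidence interval, and keep the t-test on change as a sensitivity analysis. The model should be fixed in advance, because choosing between the two after seeing results would invite selective reporting. Using the same model for the secondary efficacy measures is optional.

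The cost is one sentence and one degree of freedom, with a loss of about 3% of variance at worst. No new data, visits or participants are needed, and the number randomised stays at 44.
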